10.8. Other Analyses

The GSK's quadrivalent seasonal influenza vaccine batch numbers administered during the study vaccination period will be tabulated by ISO week, overall and by country, on the Exposed Set.

The percentage of subjects who returned the ADR card will be tabulated by centre, country and overall on the Safety Set.

As a sensitivity analysis, the analysis of AEIs and/or other AEs reported using ADR cards will also be performed on the Solicited Safety Set.

SAEs occurring within 7 days post vaccination (i.e., the day of vaccination and the following 6 days) and assessed as related to GSK's quadrivalent seasonal influenza vaccine will be described in detail.

The percentage of subjects who received co-administered vaccination on the same day as their GSK's quadrivalent seasonal influenza vaccine will be tabulated by GSK's quadrivalent seasonal influenza vaccine dose, overall and by country.

10.9. Interpretation of Analyses

All analyses will be descriptive.

10.10. Conduct of Analyses

Any deviation(s) or change(s) from the original statistical plan outlined in this protocol will be described and justified in the final study report.

10.10.1. Sequence of analyses

Three interim analyses and a final analysis will be performed.

- The *first* interim analysis will be performed by mid-November 2018
- The *second* interim analysis will be performed by end-November 2018
- The *third* interim analysis will be performed by mid-December 2018
- The final analysis will be performed when all data up to the end of the study will be available and cleaned

10.10.2. Statistical considerations for interim analyses

The interim analyses will be generated to evaluate the trend of reporting of AEs (i.e. safety monitoring) and will be performed on data which are cleaned as much as possible.

The following analyses will be performed for each interim analysis, overall and by country:

- The number of subjects vaccinated with GSK's quadrivalent seasonal influenza vaccine during each ISO week will be tabulated overall, by age strata and risk status.
- Demographic characteristics (age at study vaccination in years, gender, race) will be summarised using descriptive statistics.
- The weekly percentage of subjects reporting AEs and/or other AEs within 7 days post-vaccination period (i.e., the day of vaccination and the following 6 days) using ADR cards will be estimated by MedDRA Preferred Term, with 95% CI.

Since there is no hypothesis testing, no adjustment of type I error will be needed.

No study report will be written for the interim analyses.

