- Epoch 001: Prospective data collection starting at Visit 1 (Day 1) and ending at Visit 2 (Day 8 or when the ADR card is returned by mail) for all subjects who have previously been vaccinated against influenza in preceding seasons or aged ≥ 9 years at the time of vaccination, or ending at Visit 4 (Day 36 or when the last ADR card is returned by mail) for children aged < 9 years who have not previously been vaccinated against influenza in preceding seasons). Subjects will have up to 14 days post vaccination to return their ADR card (at the next study visit or by mail).

Table 1 Study groups and epochs foreseen in the study

Study Groups	Number of subjects	Age (Min/Max)	Epochs
Prospective	Approximately 1000	6 months and above	Epoch 001

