10.3.3. Safety Set

The Safety Set will include all subjects from the Exposed Set who received the ADR card.

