10.3.4. Solicited Safety Set

The Solicited Safety Set will include all subjects from the Safety Set who returned the ADR card.

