10.4. Derived and Transformed Data

Demography:

- For a given subject and a given demographic variable, missing measurements will not be imputed.
- Age at the vaccination will be computed as the difference between the vaccination date and the date of birth. The age will be expressed in years.

Safety:

- Subjects who did not report an adverse event will be considered as subjects who did not experience adverse event.

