10.5. Analysis of Demographics

The number of subjects included in each analysis set will be tabulated by ISO week (expected ISO weeks 40 to 52), overall and by country.

Demographic characteristics (age at study vaccination in years, gender, race) and risk status will be summarised overall and by country using descriptive statistics for each analysis set:

- Frequency tables will be generated for categorical variables such as gender.
- Mean, standard deviation, median, minimum and maximum will be provided for continuous data such as age.

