10.7. Analysis of Secondary Objectives

The primary analysis of AEs and/or other AEs reported using ADR cards will be descriptive and will be performed on the Safety Set.

For each vaccine dose*, the weekly percentage of subjects reporting AEs and/or other AEs within 7 days post-vaccination period (i.e., the day of vaccination and the following 6 days) using ADR cards will be estimated by MedDRA Preferred Term, overall and by country, as follows:

- The denominator will be the number of subjects *from the Safety Set* vaccinated with GSK's quadrivalent seasonal influenza vaccine during the week of interest (ISO weeks 40 to 52), in a given country or for all countries.
- The numerator will be the number of subjects from the denominator who reported the AE on the ADR card within 7 days following vaccination.

In addition, for each vaccine dose*, the weekly and cumulative percentages of subjects reporting AEs and/or other AEs within 7 days post-vaccination period using ADR cards, according to MedDRA Primary System Organ Class classification, will be estimated in each country and overall, by age strata (6 months to 17 years; 18 to 65 years; >65 years) and risk status (at risk/not at risk).

* Note that a second dose of GSK's quadrivalent seasonal influenza vaccine is planned to be administered only to children aged <9 years who have not previously been vaccinated against influenza in preceding seasons.

95% CI will be computed on all estimated percentages. The method for estimating the CIs will be described in the statistical analysis plan.

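### Interim weekly AE percentages score cards still outstanding as no AE, so the newest one to two weeks can fall with no change in the true rate

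*Protocol*

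**What the plan says.** Section 10.10.2 sets the purpose of the interims: "The interim analyses will be generated to evaluate the trend of reporting of AEs (i.e. safety monitoring". Its outputs are the vaccinee count, "during each ISO week will be tabulated overall, by age strata and risk status", a demographic summary, and the weekly percentage of subjects reporting AEs by Preferred Term with a 95% CI. It names no analysis set, data cut or minimum follow-up.

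The rules that would apply are elsewhere in the protocol:

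- 10.7 takes as weekly denominator the Safety Set subjects vaccinated "during the week of interest (ISO weeks 40 to 52), in a given country or for all countries". The numerator is those who reported the AE on the card.
- 10.3.3: "The Safety Set will include all subjects from the Exposed Set who received the ADR card".
- 10.4: "Subjects who did not report an adverse event will be considered as subjects who did not experience adverse event". No exception is made for a card that is not yet due.
- Section 4: "Subjects will have up to 14 days post vaccination to return their ADR card (at the next study visit or by mail". Table 3 in 7.3 allows Visit 2 from 7 to 14 days after Visit 1.
- 10.10.1 places the interims at mid-November, end-November and mid-December 2018. All fall inside the recruitment period, which runs to 31 December.

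A set limited to returned cards exists (10.3.4: "The Solicited Safety Set will include all subjects from the Safety Set who returned the ADR card"), but 10.8 uses it only for a sensitivity analysis. Section 10.5 plans a table that would show card return by week: "The number of subjects included in each analysis set will be tabulated by ISO week". Neither is on the interim list. The card-return percentage in 10.8 is by centre, country and overall, not by week.

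**The concern.** At an interim, a subject vaccinated a few days earlier is already in the denominator but can hardly be in the numerator, because the 7-day card is not yet complete. Under 10.4 that subject counts as free of AEs. The same holds for anyone whose card is still within the 14-day return window. The newest weeks are therefore biased downward in a table meant to show a trend.

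The glossary describes enhanced safety surveillance as detecting an increase in near real-time. A downward artefact in the latest cohorts works against that aim: a real rise can be masked, and a flat rate can look like a fall. The reader of the interim tables cannot correct for it, because vaccinees are shown by week but returned cards are not.

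**Working it through.** **The plan's own weekly figures.** Table 4, 75 subjects per week, all countries:

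- True 10%: RSE = √(0.10 × 0.90 / 75) / 0.10 = 34.6%; exact 95% CI 4.27 to 19.12.
- True 1%: probability of at least one case = 1 − 0.99^75 = 52.9%.

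All agree with the printed values. They presume that all 75 outcomes are known.

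**Inputs.** From the protocol: 75 vaccinees per week (10.2); cards back by day 14 (section 4); Visit 2 at 7 to 14 days (Table 3). Assumed, because the protocol does not say: cuts on Thursday 15 November, Friday 30 November and Saturday 15 December 2018; vaccinations included to the cut; vaccination evenly on 7 days a week; every card eventually returned, on days 7 to 14; no entry lag.

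**Formula.** For a dose given on day d, lag = cut − d. The card is in hand if lag ≥ 7 (earliest return) or lag ≥ 14 (latest return). With even returns the probability is min(max(lag − 6, 0), 8) / 8. Average over the days of the ISO week. Expected observed percentage = true percentage × share in hand.

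Example, 15 November, week 45 (lags 10 to 4):

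- earliest 4/7 = 0.57
- latest 0
- even (4 + 3 + 2 + 1) / (8 × 7) = 0.18

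| Assumed cut | Newest week | Week before | Third week back |
|---|---|---|---|
| 15 Nov | W46: 0 | W45: 0–0.57 (even 0.18) | W44: 0.57–1.00 (0.89) |
| 30 Nov | W48: 0 | W47: 0–0.71 (0.27) | W46: 0.71–1.00 (0.95) |
| 15 Dec | W50: 0 | W49: 0–0.86 (0.38) | W48: 0.86–1.00 (0.98) |

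**Variations.**

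- Weekday-only vaccination, even returns: the third week back is 0.975, 1.00 and 1.00, so in practice two weeks are affected.
- Sunday cut: at most two weeks are affected, at 0 and then 0–1.00 (even 0.50). In the even case a doubling from 10% to 20% would show as 10% in the second-newest week.
- Entry lag of 3 days: the third week back falls to 0.62, 0.73 and 0.82.

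**Doses still inside the window.** 14 days × 75/7 = 150 at each cut. With accrual from 1 October, the totals are 46, 61 and 76 days × 75/7 = 493, 654 and 814. The open shares are 30%, 23% and 18%. The amendment rationale expects most recruitment from mid-October. Starting on 15 October, the first interim would have 32 × 75/7 = 343 doses, of which 150 (44%) are open.

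**What a reader would see.** Constant true 10%, cut 15 November, even returns: 10%, 8.9%, 1.8% and 0% for weeks 43 to 46.

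- Week 46 to Thursday holds 4 × 75/7 = 43 doses. The exact 95% CI for 0/43 is 0.00 to 8.22, which excludes the true value. With complete data 0/43 would have probability 0.9^43 = 0.011.
- By country the interval still includes 10%: 0/14 gives 0.0–23.2, and a full week of 0/25 gives 0.0–13.7.
- At a true 1%, 0.99^43 = 0.65, so a zero week is unremarkable anyway.

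**Recovery.** The assumed cuts are 15 days apart, so any dose open at one cut has lag ≥ 15 at the next. It is then complete if entry lag is at most 1 day. Doses open at the third interim are completed only in the final analysis.

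**The case against.** The protocol does not say that vaccinations are included up to extraction. Sections 10.10.1 and 10.10.2 are silent on the cut, and a cut-off or minimum follow-up is normal SAP content. Section 10.10.2 also names no analysis set, so carrying over 10.7 and 10.4 is an inference. The 14-day limit has no lower bound and cards can be mailed, so some may arrive before day 7. The tables are descriptive, with no test, stopping rule or interim report.

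Part of this stands. The finding is conditional on where the tables stop, near 0% is more accurate than exactly 0%, and the shares are illustrative because return timing and accrual are assumed.

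The SAP argument does not remove the point. The protocol itself fixes the Safety Set, the weekly denominator, the rule for non-reporters and the list of interim outputs, and those together create the bias. It expressly defers the CI method to the SAP, but not the handling of cards not yet due. The 10.7 denominator is the only weekly one available to an interim programmer.

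**Conclusion.** The concern holds and should be fixed. If interim tables run to the extraction date, the protocol's rules put the newest ISO week near 0% and usually dilute the week before, at a constant true rate. A third week is affected only with a mid-week cut and late returns, or with entry lag. On the stated assumptions, 150 doses are unresolved at each interim, which is 18% to 30% of those given, or 44% at the first interim if accrual starts on 15 October.

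The reach is limited. Older weeks are unaffected. Open doses fill in by the next interim on the assumed cuts, or at the final analysis for the third. Final results and the 24-hour route for vaccine-related SAEs (8.2) are untouched. The distortion is visible mainly for very common events with all countries combined. The effect would not arise if the tables stopped about two weeks before extraction, but nothing in the protocol requires that.

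**What to change.** Add three sentences to 10.10.2:

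1. State a data cut for each interim.
2. Compute Safety Set weekly percentages only for doses given at least 14 days before the cut, plus any card-entry lag.
3. For later doses, show by ISO week the Safety Set and Solicited Safety Set counts (the 10.5 table, run at the interims), with AEs already reported on returned cards by Preferred Term, flagged as immature.

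The third item ensures that no report in hand is hidden. On the assumptions above it keeps visible 0 to 75 returned cards from the 150 open doses: 75 with earliest returns, 0 with latest, and (1 + 2 + … + 7)/8 × 75/7 = 38 with even returns.

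The cost is a date filter and a rerun of a table already planned; no new data are needed. The downside is that percentages for the newest two to three weeks wait until the next interim or the final analysis. With accrual from 15 October, the first interim would have percentages for 343 − 150 = 193 doses (weeks 42, 43 and part of 44). The partial ISO week is harmless, because numerator and denominator are filtered alike.

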1. INTRODUCTION

Influenza is an acute, highly contagious, respiratory disease caused by influenza viruses, mainly spread through respiratory droplets. The illness is accompanied by fever and variable degrees of other systemic symptoms, ranging from mild fatigue to respiratory failure and even death.

Influenza is a major public health burden. It is responsible for 50 million disease episodes and 15,000 to 70,000 deaths in the EU/EEA each year, although with considerable variation from season to season [Uhart, 2016] and by methodology used [Nicoll, 2012]. Influenza occurs in annual epidemics that are associated with significant morbidity and mortality and have substantial public health impact, in particular in the elderly and in children younger than one year of age [Zhou, 2012]. In the US, approximately 9.2 to 60.8 million people contract influenza annually, resulting in an average of 140,000 to 710,000 hospitalisations and 12,000 to 56,000 deaths [CDC, 2016a].

Annual influenza vaccination is the most effective measure to reduce the risk of influenza infection and its complications [Foppa, 2015]. During the 2015-2016 influenza season, CDC estimated that the overall influenza vaccination coverage among all people ≥ 6 months of age was 45.6%. It prevented almost 5 million influenza illnesses, 2.5 million medical visits to health providers, 71,000 hospitalizations, and 3,000 deaths [CDC, 2016b]. However, due to frequent genetic and antigenic changes in influenza viruses, seasonal vaccines are frequently reformulated with updated viral strains based on annual World Health Organization (WHO) recommendations [WHO, 2018]. Therefore, there is a need for constant benefit-risk monitoring of these vaccines.

The European Medicines Agency (EMA) has released guidance on enhanced safety surveillance for seasonal influenza vaccines in the European Union (EU) [EMA, 2014; EMA, 2016], replacing the annual evaluation of safety and immunogenicity of seasonal influenza vaccines in small scale clinical trials since 2015. This guidance sets out new standards for surveillance that all Marketing Authorisation Holders (MAHs) of vaccines in the EU must address. The key objective of the EMA enhanced safety surveillance is to rapidly detect a significant increase in the frequency and/or severity of expected reactions (local, systemic or allergic reactions) that may indicate a potential risk.

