10. STATISTICAL METHODS

10.1. Endpoints

10.1.1. Primary endpoint

- Occurrence of AEs and/or other AEs within 7 days post each GSK's quadrivalent seasonal influenza vaccination (i.e., the day of vaccination and the following 6 days) reported using ADR cards, according to MedDRA classification, by cumulative weeks (expected ISO weeks 40 to 52).

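### The three interim safety looks report only weekly AE percentages and omit the cumulative percentage, which is the primary endpoint and much more precise

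*Protocol*

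**What the plan says.** Section 10.10.1 plans interim analyses by mid-November, end-November and mid-December 2018. Section 10.10.2 gives their purpose: "The interim analyses will be generated to evaluate the trend of reporting of AEs (i.e. safety monitoring"). It then fixes their content: "The following analyses will be performed for each interim analysis, overall and by country". Three outputs follow:

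- the number of subjects vaccinated, which "during each ISO week will be tabulated overall, by age strata and risk status";
- demographic summaries;
- "The weekly percentage of subjects reporting AEs and/or other AEs within 7 days post-vaccination period", by Preferred Term with 95% CI.

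Only the third concerns adverse events. It is weekly, and it is not split by age or risk status.

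The primary endpoint in Section 10.1.1 is on a different scale: "by cumulative weeks (expected ISO weeks 40 to 52"). Section 10.6 estimates it by Preferred Term, overall and by country, up to each study week. For the secondary objectives, Section 10.7 adds weekly and cumulative percentages by System Organ Class that "will be estimated in each country and overall, by age strata (6 months to 17 years; 18 to 65 years; >65 years") and by risk status. Section 10.10.2 brings neither the 10.6 output nor the stratified 10.7 output into the interims.

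**The concern.** Section 1 describes the aim of this kind of surveillance as to "rapidly detect a significant increase in the frequency and/or severity of expected reactions". Completion of the final statistical analysis is planned for 19 April 2019 (Section 11), well after the vaccination period. The interims are therefore the only planned aggregate look at event frequency while vaccination is under way. At those looks, the single listed event estimate rests on about 75 subjects per week overall and 25 per week in each country. Table 5 was built to show how the cumulative estimate tightens as the study runs, yet no interim output reports that estimate. What is at stake is how readily an increase in common or fairly common reactions can be told from noise at the interims.

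**Working it through.** **Inputs.** Weekly n is 75 (all countries) and 25 (by country), from Table 4. Cumulative n by week and the 1% reference rate come from Table 5. Card return takes up to 14 days (Section 4). The rationale for Amendment 1 expects most recruitment from mid-October.

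**Formulas.** P(at least one case) = 1 − (1 − p)^n. RSE = √[(1 − p)/(n·p)]. Intervals are Clopper-Pearson.

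**Reproducing the protocol's figures, p = 1%.**

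- Weekly, all countries, n=75: P = 1 − 0.99^75 = 52.9%; RSE = √(0.99/0.75) = 114.9%; Table 4 interval 0.01 to 6.65%.
- Cumulative weeks 40-45, n=450: P = 1 − 0.99^450 = 98.9%; RSE = √(0.99/4.5) = 46.9%; Table 5 interval 0.24 to 2.26%.
- Weekly, by country, n=25: P = 22.2%; RSE = √(0.99/0.25) = 199.0%.
- Cumulative weeks 40-45, by country, n=150: P = 77.9%; RSE = √(0.99/1.5) = 81.2%.

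All agree with Tables 4 and 5. The ratio 114.9/46.9 = 2.45 is √6, the gain from six equal weeks.

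**A pessimistic timing.** Mid-November, end-November and mid-December fall in ISO weeks 46, 48 and 50. Assume that recruitment starts in week 42 at 75 per week, that the week of the look is incomplete, and that the two weeks before it still have cards outstanding.

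| Look | Usable weeks | Cumulative n | RSE at 1% |
|---|---|---|---|
| Mid-November | 42-43 | 150 | 81.2% |
| End-November | 42-45 | 300 | 57.4% |
| Mid-December | 42-47 | 450 | 46.9% |

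Each is below the 114.9% of a single week.

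**What this means for detecting a rise (illustration).** The protocol sets no baseline or flag. Assume a known baseline and an exact one-sided 2.5% flag. A rate of 4% against a baseline of 2% is flagged with probability 0.18 in one week (n=75, flag at 5 cases) and 0.72 cumulatively (n=450, flag at 16). For 10% against 5% the probabilities are 0.33 and 0.98. This supposes that the raised rate holds from the start of the season.

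**Age strata.** The protocol does not state stratum shares. Assuming 10% or 20% children at a cumulative n of 525 (weeks 40-46):

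- n=52: RSE = √(0.99/0.52) = 138%.
- n=105: RSE = √(0.99/1.05) = 97%.

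A weekly split at the same shares (n=8 or 15) gives 352% or 257%.

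**The case against.** **The weekly series fits the stated purpose.** The interims are meant to show trend, and a cumulative figure averages a late change into earlier weeks. This stands. The gap is the missing cumulative figure, not the presence of the weekly one.

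**The cumulative figure can nearly be rebuilt.** Each interim shows the weekly series to date and the weekly counts vaccinated, so multiplying and summing comes close, apart from small differences from the Safety Set denominator. The unseen SAP might also list more tables. This softens the point. But a hand-built sum is not planned output and carries no interval, and the protocol fixes the interim content itself.

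Stronger readings a reader might infer, and why the protocol does not support them:

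- *That the interims use the least informative estimate possible.* They use the less precise of the two all-age estimates. A weekly age-stratified figure would be less precise still.
- *That nothing else could catch a problem early.* Under Section 8.2, vaccine-related serious events go to the sponsor within 24 hours and routine reporting continues. Section 8 also tells subjects to contact the investigator immediately about worrying symptoms. None of this measures the frequency of expected, mostly non-serious reactions.
- *That a rise in children would be lost among adults.* Suppose 10-20% children, child fever going from 5% to 10%, and adults at 1%. The pooled figure then moves only from 1.4% to 1.9%, or from 1.8% to 2.8%. But output is also by country and only Spain enrols children. If Spain enrols about 333 of 1000, children are about 30-60% of its subjects, and the Spanish figure moves from 2.2% to 3.7%, or from 3.4% to 6.4%. Spain also enrols adults up to 65, so some dilution remains, but the pooled row overstates it.

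**Conclusion.** The point holds as an omission from Section 10.10.2. The cumulative percentage, which is the primary endpoint, is absent from the three looks intended for safety monitoring. By the protocol's own tables it is about 2.4 times as precise as a single week once six weeks have accrued. With a late start and outstanding cards, the gain is about 1.4, 2.0 and 2.4 times at the three looks (114.9 divided by 81.2, 57.4 and 46.9). The ratios depend on even weekly accrual; the late-start figures also depend on the timing assumptions above.

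The case for an age split is weaker. It rests on finding a signal confined to one age group, needs cumulative data, and gives wide intervals even then. It is a supportive addition only.

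The consequence is confined to the interims. There is no hypothesis test, and the final primary and secondary estimates are untouched.

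**What to change.** In Section 10.10.2, add to the list for each interim the cumulative percentage of subjects reporting events by MedDRA Preferred Term with 95% CI, overall and by country, defined as in Section 10.6. Present it next to the weekly series, which stays.

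As a supportive addition, give the cumulative percentage by age stratum for all countries together, at the System Organ Class level already planned in Section 10.7. Add a few key Preferred Terms such as pyrexia, because a System Organ Class table would not show fever on its own line. Note that the paediatric cells will be sparse.

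The cost is small. The all-age cumulative table and the System Organ Class table by age are already planned for the final analysis and would be run at three earlier dates. Only the Preferred Term lines by age are new. No extra data are collected, and no type I error adjustment arises because nothing is tested. The downside is a few more interim tables, with wide intervals in the age strata that should not be over-read.
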